DESKi	PROSPECTIVE EVALUATION OF HEARTFOCUS: A SOFTWARE SUPPORTING THE ACQUISITION OF CARDIAC ULTRASOUND EXAMS	HF-01 Version:4.2
-------	---------------------------------------------------------------------------------------------------------	----------------------

Protocol title	PROSPECTIVE EVALUATION OF HEARTFOCUS: A SOFTWARE SUPPORTING THE ACQUISITION OF CARDIAC ULTRASOUND EXAMS
Version Date	23/12/2023
NCT	NCT05874128

DE SKI	PROSPECTIVE EVALUATION OF HEARTFOCUS: A SOFTWARE SUPPORTING THE ACQUISITION OF CARDIAC ULTRASOUND EXAMS	HF-01 Version:4.2
---------------	----------------------------------------------------------------------------------------------------------------	------------------------------------

PRIMARY HYPOTHESIS	
The primary hypothesis is that novices without previous experience in ultrasound examination could obtain diagnostic-quality acquisitions with the software HeartFocus.

OBJECTIVES	
The primary objective of the study is to evaluate if ultrasound exams, performed with the HeartFocus software by novices, nurses without prior ultrasound experience, are of sufficient quality to analyze visually:
 
 
• The left ventricular size,
 
• The left ventricular function,
 
• The right ventricular size,
 
• The presence of non-trivial pericardial effusion.
 
 
The secondary objectives are:
 
 
• To evaluate the agreement between the acquisitions obtained by experts and those obtained by novices in terms of quality and echocardiographic parameters (secondary endpoints 1 to 4)
 
• To evaluate the impact of the investigating centers, prior cardiac diagnoses, and obese patients on the quality of ultrasound exam
 
• To evaluate the time to acquire a limited ultrasound exam for a novice with the HeartFocus software.
 
• To evaluate the performance of HeartEF, to automatically calculate the ejection fraction
 

NUMBER OF SUBJECTS	
240 patients will be included, 120 in Site 01 and 120 in Site 2
 
As part of their training, novices will practice cardiac ultrasound acquisition on 72 patients (36 in Site 01 and 36 in Site 2). Those patients will be not included in the analysis. They will sign a different consent form.

STUDY DURATION	
 
• Length of inclusion period: 5 months
 
• Duration of follow-up per participant / inclusion for the training: approximately 30 additional minutes
 
• Duration of follow-up per participant / inclusion for the analysis: approximately 40 additional minutes
 
• Total research duration: 5 months for inclusion + 5 months for outcome analysis.
 

STUDY DESIGN	
This prospective multicentric international non inferiority pivotal investigation will evaluate the ability of the Heartfocus software in

	
supporting novices for the acquisition of 10 reference views of cardiac ultrasound. The 10 reference views are the following:
 

• Parasternal long axis,

• Parasternal short axis at the aortic valve,

• Parasternal short axis at the mitral valve,

• Parasternal short axis at the papillary muscles,

• Apical 5-chamber,

• Apical 4-chamber,

• Apical 3-chamber,

• Apical 2-chamber,

• Subcostal 4-chamber,

• Subcostal inferior vena cava.

 
Novices will be nurses without prior ultrasound experience who have received dedicated training on cardiac ultrasound and on Heartfocus software.
 
Patients included in the study will be adult patients scheduled for an echocardiogram at one of the two investigating centers. Ultrasound exams will be limited to the acquisition of 10 reference views (Table 1).
 
Patients will receive 2 additional limited exams, which consist of the acquisition of ultrasound clips for each of the 10 references views:
 

• one by a novice, nurses having received a dedicated training of 2 days, with the Clarius phased array probe and the HeartFocus software with the guidance system,

• one by an expert (experienced sonographer cardiologist) with the Clarius phased array probe and the HeartFocus software without the guidance system.

 
A total of 8 novices will perform the acquisition on 30 different patients each. In total 240 patients will be included in the analysis, half in each investigator center. The exams (240 acquired by novices, 240 by experts) will be assessed by a review committee, composed by 5 different cardiologists.
 
Each exam will be reviewed by all 5 cardiologists from this committee.
	
INCLUSION CRITERIA	

• Patient (male or female) over 18 years old,

	

	
 
• Patient having an echocardiography examination scheduled in one of the two investigation centers,
 
• Patient who has given his consent to participate in the research and signed consent form,
 
• Social security affiliation (for France only).
 
	
EXCLUSION CRITERIA	
 
• Patient subject to a measure of legal protection (safeguard of justice, guardianship, or curatorship),
 
• Patient deprived of liberty by judicial or administrative decision,
 
• Patient being unable to give his consent,
 
• Pregnant or breastfeeding women (declarative),
 
• Patient with cardiac anatomy that does not allow reference electrocardiographic sections to be made (situs inversus, single ventricle, congenital anomalies, etc),
 
• Patient having benefited from prior echocardiographic exams whose reports mention poor or weak echogenicity,
 
• Patient having known chest deformity that has already been mentioned in previous reports or has been the subject of investigations (pectum excavatum),
 
• Patient who has undergone total or partial pneumonectomy.
 
	
ENDPOINTS	
All endpoints will be assessed by 5 different cardiologists, from the review committee. The criteria will be assessed on the exams obtained by novices and those obtained by experts, for each patient. Cardiologists will not know if the exam was performed by a novice or an expert.
 
Primary endpoints:
 
The cardiologists will evaluate whether the ultrasound exam performed has sufficient quality to visually analyze (binary yes/no) :
 
 
• The left ventricular size (yes/no)
 
• The left ventricular function (yes/no)
 
• The right ventricle size (yes/no)
 
• The presence of non-trivial pericardial effusion (yes/no)
 
 
Secondary endpoints:
 
1- The cardiologists will evaluate whether the ultrasound exam performed has sufficient quality to visually analyze (binary yes/no):
 
 
• The function of the right ventricle?
 
• The size of the inferior vena cava?
 
• The size of the left atrium?
 
	

- The aortic valve?
- The mitral valve?
- The tricuspid valve?
- The segmental kinetics?

2- The cardiologists will evaluate whether the quality of each clip is good enough for their interpretation (binary yes/no) (Yes : ACEP $\geq$  3)..

3- The cardiologists will determine on the ultrasound measurements: (qualitative yes/no)

- Is there a left ventricular hypertrophy?
- Is there a right ventricular hypertrophy?
- Is there a dilation of the left ventricle?
- Is there a dilation of the right ventricle?
- Is there a dilation of the left atrium?
- Is there a dilation of the right atrium?
- Is there an abnormal left ventricular function?
- Is there an abnormal right ventricular function?
- Is there an abnormal mitral valve?
- Is there an abnormal tricuspid valve?
- Is there an abnormal aortic valve?
- Is there a pericardial effusion?
- Is there a dilatation of the inferior vena cava?
- Is there a kinetic disorder?
- Is there another abnormality? (comments)

4- The cardiologists will determine on the acquisitions the following ultrasound measurements (quantitative)

- Left ventricular
  - End-systolic and end-diastolic volumes
  - Left ventricular function.
  - Left ventricular parameters will be assessed by cardiologists using the Simpson Biplane method and through the HeartEF algorithm developed by DESKi.
- Parasternal analysis
  - Septal wall thickness
  - Posterior wall thickness
  - Internal diameter of the left ventricle (systole and diastole)

DESKI	PROSPECTIVE EVALUATION OF HEARTFOCUS: A SOFTWARE SUPPORTING THE ACQUISITION OF CARDIAC ULTRASOUND EXAMS	HF-01 Version:4.2
-------	---------------------------------------------------------------------------------------------------------	----------------------

	
 
○ Aortic diameter
 
● Diameter of the inferior vena cava
 
 
5- The acquisition time for the limited ultrasound exam

MEDICAL DEVICES / CLINICAL INVESTIGATION STRATEGIES /PROCEDURES	
The HeartFocus software has not yet obtained the FDA or CE certification. This clinical trial aims to collect clinical evidence for FDA and CE certification.
 
The device is classified as Class IIa - software under MDR in Europe and Class II in US following FDA classification.
 
HeartFocus software is compatible with the ultrasound probe Clarius phased array. This probe has received FDA certification and CE certification.

ANALYSIS	
Patient description: The population will be described in terms of demographics, ultrasound parameters, and pathology.
 
Endpoints: For all quality criteria, the percentage of success and its confidence interval will be evaluated for acquisitions performed by experts and acquisitions performed by novices. This analysis will be performed via a multi-reader, multi-case power analysis.
 
For each qualitative ultrasound measurement, taking into account the experts' acquisition as the reference, the following parameters will be evaluated:
 
 
● Percentage of agreement
 
● Sensitivity
 
● Specificity
 
● Precision
 
● Recall
 
● F1-score
 
● Area under the curve
 
 
For each quantitative ultrasound measurement:
 
 
● The mean, standard deviation and 95% confidence interval of the difference will be calculated between the measurements made on the acquisitions obtained by the experts and those obtained by the novices
 
● Bland-Altman plots and correlation plots will be performed.
 
 
Sensitivity studies will be performed on the investigating centers, prior cardiac diagnoses, and obese patients.

DESKi	PROSPECTIVE EVALUATION OF HEARTFOCUS: A SOFTWARE SUPPORTING THE ACQUISITION OF CARDIAC ULTRASOUND EXAMS	HF-01 Version:4.2
-------	---------------------------------------------------------------------------------------------------------	----------------------

	The evaluation of HeartEF will be performed by comparing the results from the algorithm to the manual cardiologist's analysis.
--	--------------------------------------------------------------------------------------------------------------------------------

EXPECTED IMPACTS	
From a medical point of view, there will be no direct benefit for the patient included in the analysis.
 
At a larger scale, HeartFocus software will outlook access to ultrasound exams by allowing non-experts (emergency physicians, residents, general practitioners, paramedics, and nurses) to acquire cardiac ultrasound exams of sufficient quality for their analysis, without any previous experience in echography.
 
This would improve patient management by optimizing the care pathway, with echography being used as a screening or follow-up tool for patients.

------------------	---------------------------------------------------------------------------------------------------------------------------------------------------------------------------------------------------------------------------------------------------------------------------------------------------------------------------------------------------------------------------------------------------------------------------------------------------------------------------------------------------------------------------------------------------------------------------------------------------

2.1 Study Design

This prospective multicentric international non-inferiority pivotal investigation will evaluate the ability of the Heartfocus software to support novices for the acquisition of 10 reference views of cardiac ultrasound. The 10 reference views are the following:

- apical 2-chamber (A2C),
- apical 3-chamber (A3C),
- apical 4-chamber (A4C),
- apical 5-chamber (A5C),
- parasternal long axis (PLAX),
- parasternal short axis at the aortic valve (PSAX-AV),
- parasternal short axis at the mitral valve (PSAX-MV),
- parasternal short axis at the papillary muscles (PSAX-PM),
- subcostal 4-chamber (SC-4C),
- subcostal inferior vena cava (SC-IVC).

Novices will be nurses without prior ultrasound experience who have received dedicated training on cardiac ultrasound and Heartfocus software.

Patients included in the study will be adult patients scheduled for an echocardiogram at one of the two investigating centers. Each patient included in the study will receive a standard cardiac ultrasound exam performed in the standard way with the regular ultrasound system used in the cardiologic service.

Patients will receive 2 additional limited exams to their standard exam, which consist of the acquisition of ultrasound clips for each of the 10 reference views:

- one by a novice, *i.e.* nurses having received a dedicated training of 2 days, with the Clarius phased array probe and the HeartFocus software with the guidance system,
- one by an expert (experienced sonographer cardiologist) with the Clarius phased array probe and the HeartFocus software without the guidance system.

A total of 8 novices will perform the acquisition on 30 different patients each. In total 240 patients will be included in the analysis, half in each investigator center. The exams (240 acquired by novices, 240 by experts) will be assessed by an independent review committee, composed of 5 different cardiologists. Each exam will be reviewed by all 5 cardiologists from this committee. Cardiologists will not know if the exam was performed by a novice or an expert. Cardiologists will be blinded to the investigating center in which the acquisition has been performed.

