2.3.2 Exclusion Criteria

The exclusion criteria are:

- patient subject to a measure of legal protection (safeguard of justice, guardianship, or curatorship),
- patient deprived of liberty by judicial or administrative decision,
- patient unable to give his consent,
- pregnant or breastfeeding women (declarative),
- patient with cardiac anatomy that does not allow reference electrocardiographic sections to be made (situs inversus, single ventricle, congenital anomalies, etc.),
- patient having benefited from prior echocardiographic exams whose reports mention poor or weak echogenicity,
- patient having known chest deformity that has already been mentioned in previous reports or has been the subject of investigations (*pectum excavatum*),
- patient who has undergone total or partial pneumonectomy.

3. Study Objectives

The primary hypothesis is that novices without previous experience in ultrasound examination could obtain diagnostic-quality acquisitions with the software HeartFocus.

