3.1 Primary Objective

The primary objective of the study is to evaluate if ultrasound exams, performed with the HeartFocus software by novices (nurses without prior ultrasound experience), allow the qualitative visual assessment of

- left ventricular size,
- global left ventricular function,
- right ventricular size,
- non-trivial pericardial effusion.

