3.2 Secondary Objectives

The secondary objectives are:

- to evaluate the agreement between the acquisitions obtained by experts and those obtained by novices in terms of quality and echocardiographic parameters,
- to evaluate the impact of the investigating centers, prior cardiac diagnoses, and obese patients on the quality of ultrasound exams,
- to evaluate the time to acquire a limited ultrasound exam for a novice with the HeartFocus software,
- to evaluate the performance of HeartEF to automatically calculate the ejection fraction.

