3.3 Primary Endpoints

The entire exam allows the qualitative visual assessment of

- left ventricular size (yes, no),
- global left ventricular function (yes, no),
- right ventricle size (yes, no),
- non-trivial pericardial effusion (yes, no).

All endpoints will be assessed by 5 different cardiologists, from the independent review committee. The criteria will be assessed on the exams obtained by novices and those obtained by experts, for each patient.

Success Criteria

The lower limit of the 95% confidence interval (CI) around the percentage of exams that have sufficient quality to allow the qualitative visual assessment of

- left ventricular size,
- global left ventricular function,
- right ventricle size,
- and non-trivial pericardial effusion

are all strictly above 80%.

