3.5 Sample Size Justification

The main hypothesis for the sample size calculation is based on the sequential testing of the four primary endpoints (the left ventricular size, the left ventricular function, the size of the right ventricle, and the presence of non-trivial pericardial effusion) with the performance goal of 80% (each lower 2-sided 95% CI limit for each parameter should be greater than 80%).

As the study design is like the pivotal trial, conducted by a US team, which led to FDA certification of our competitor software to assist novices in performing cardiac ultrasound acquisitions, we based our sample size calculation on the sample size calculation of the pivotal trial. This pivotal trial included 240 patients and 8 different operators. Each operator performed the acquisitions on 30 patients.

The elements for the sample size calculation of the pivotal study are described below:

- the pivotal study was powered to detect the primary endpoint's exceeding the performance goal of 80% ($\alpha = 0.05$, $\beta = 0.2$),
- the statistical power was estimated using iMRMC 4.0 software developed by the FDA, which provides the 95% CI around the point estimate for a given parameter and was used for the primary endpoint analysis,
- the sample size (240 patients and 8 different operators who performed the acquisitions on 30 patients) would have a statistical power of 0.98 for each parameter or greater than 0.92 for 4 sequentially tested parameters.

4. Statistical Methodology

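### The trial is labelled non-inferiority, but the plan tests only an 80% performance goal and gives the novice–expert quality difference neither a margin nor an interval

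*SAP*

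**What the plan says.** Both documents put non-inferiority in the design statement. The protocol synopsis, under Study Design, has "This prospective multicentric international non inferiority pivotal investigation will evaluate the ability of the Heartfocus software in" and SAP 2.1 has "This prospective multicentric international non-inferiority pivotal investigation will evaluate the ability of the Heartfocus software to support novices".

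The rest of the plan describes a different kind of test:

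- **Hypothesis (SAP 3):** "The primary hypothesis is that novices without previous experience in ultrasound examination could obtain diagnostic-quality acquisitions with the software HeartFocus". No comparator is named.
- **Primary objective (SAP 3.1):** to "evaluate if ultrasound exams, performed with the HeartFocus software by novices (nurses without prior ultrasound experience), allow the qualitative visual assessment of" four features. Again this concerns novice exams only.
- **Success criteria (SAP 3.3):** the lower 95% limits for the four percentages "are all strictly above 80" per cent.
- **Sample size (SAP 3.5):** four endpoints tested sequentially "with the performance goal of 80% (each lower 2-sided 95% CI limit for each parameter should be greater than 80" per cent).
- **First secondary objective (SAP 3.2):** "to evaluate the agreement between the acquisitions obtained by experts and those obtained by novices in terms of quality and echocardiographic parameters".
- **Analysis of primary and quality endpoints (SAP 5.4.1 and 5.4.2.1):** the novice and expert percentages each get a 95% CI from a multi-reader multi-case (MRMC) analysis. The difference, in patients with both exams, is simply computed.
- **Protocol, Analysis:** for quality criteria, "the percentage of success and its confidence interval will be evaluated for acquisitions performed by experts and acquisitions performed by novices". That is one interval per group and none for the contrast.

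SAP 5.4.2.3 does specify a 95% CI of the difference for the quantitative measurements.

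**The concern.** A non-inferiority trial needs a comparator, a margin, and an interval or test for the difference. The documents have the comparator, since each patient also has an expert exam, but neither of the other two. The design statement therefore claims a property that the plan lacks.

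Two things are at stake. First, the protocol says the trial is meant to provide evidence for FDA and CE certification. A pass on the 80% goal under a non-inferiority label could be taken as non-inferiority to experts, which was never tested. Second, the quality part of the first secondary objective would rest on a point difference with no statement of its precision. A reader could approximate an interval from the two group CIs only by assuming that the exams are independent, although they are paired. That also requires both percentages to come from the same patients. The full analysis set (SAP 4.2.3) requires only the novice exam, while the comparison requires both.

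**Working it through.** **1. The plan's own figure.** SAP 3.5 gives power 0.98 per parameter and more than 0.92 for four. Under independence 0.98⁴ = 0.922, which agrees. The calculation concerns the 80% goal and does not use the expert exams.

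**2. Do the general conventions fill the gap?** SAP 4.1 sets the confidence level, gives exact intervals for single proportions, and lists χ² or Fisher tests. None of these is an interval for a paired difference in proportions. SAP 5.4.2.2 gives a CI for overall agreement, but that concerns the clinical reading (for example normal or reduced), not whether the exam was good enough to read.

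**3. What passing requires.** With n = 240 and Clopper–Pearson limits, 204/240 (85.0%) has a lower limit of 79.8% and fails; 205/240 (85.4%) has 80.3% and passes. The expert result does not enter. An MRMC or clustered interval would move this cut-off.

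**4. What the missing interval could show.** The documents give no expected rates, correlations or ICCs, so these are assumptions: novices 90%, experts 97%, within-patient correlation φ. Reader variance is not modelled.

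The proportion with both exams adequate is p₁₁ = pₙpₑ + φ√[pₙ(1−pₙ)pₑ(1−pₑ)]. The discordant proportions are b = pₙ − p₁₁ and c = pₑ − p₁₁, and SE = √[(b + c − (b − c)²)/n].

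At φ = 0.2: p₁₁ = 0.873 + 0.2 × 0.0512 = 0.8832, b = 0.0168, c = 0.0868, so SE = √[(0.1035 − 0.0049)/240] = 2.03 points.

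| φ | SE (points) | 95% CI of −7.0 |
|---|---|---|
| 0 | 2.23 | −11.4 to −2.6 |
| 0.2 | 2.03 | −11.0 to −3.0 |
| 0.4 | 1.80 | −10.5 to −3.5 |

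Each of the 8 novices scans 30 patients. For clustering by novice, multiply the SE by √(1 + 29 × ICC) and use t on 7 df (2.365). At φ = 0.2:

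- ICC 0.02: 2.03 × √1.58 = 2.55 points; CI −13.0 to −1.0.
- ICC 0.05: 2.03 × √2.45 = 3.17 points; CI −14.5 to +0.5.

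**5. How often a pass would coincide with a detectable deficit.** This is the simulated chance that one endpoint passes 80% while the paired 95% CI lies wholly below zero (true novice rate 90%, φ = 0.2). The first row uses 200,000 multinomial samples, the exact limit and a paired Wald interval. The other rows use 100,000 trials of 8 × 30, with t intervals (7 df) on novice-level means.

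| Model | Experts 93% | 95% | 97% | 99% |
|---|---|---|---|---|
| No clustering, unclustered analysis | 26% | 65% | 94% | 99% |
| Novice-level analysis, ICC 0 | 20% | 51% | 85% | 97% |
| ICC 0.02 | 12% | 31% | 61% | 85% |
| ICC 0.05 | 6% | 17% | 37% | 64% |

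In the ICC 0.02 and 0.05 rows the paired outcomes are clustered (Dirichlet-multinomial). If only the novice outcome is clustered, the figures are 12/33/65/86% at ICC 0.02 and 5/17/41/66% at ICC 0.05.

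**The case against.** The strongest reply is that the operative plan is clear. Hypothesis, objective, success rule and sample size all point to the 80% goal, no passage says success will be reported as non-inferiority to experts, and the difference is introduced only for comparison, with no decision attached. This is right as far as it goes: the primary test is sound on this point and no planned decision changes. It does not remove a design label in both documents that the plan does not support.

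Second, an interval wholly below zero is a detectable deficit, not failed non-inferiority. In the unclustered 97% case, the joint chance is about 94%. In about 91 of those 94 percentage points the lower limit also lies above −15 points, and in about 30 it lies above −10 (margins assumed only for illustration). This stands. The table shows how often a pass and a deficit could coexist; it does not show how often a non-inferiority claim would be false, which cannot be worked out without a margin. The figures also range from 5% to 99% over assumed inputs, so they are illustrations.

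Third, assuming independence costs little for pairing alone: 0.4 points per limit between φ = 0 and φ = 0.2. This is also true, but it leaves shared readers, clustering by novice and possibly different patient sets unaddressed.

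Fourth, the public protocol is a synopsis, and a margin may exist in the full text. That is possible, and the fix allows for it. The SAP would still need to state the margin and its test.

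**Conclusion.** The concern holds. Both documents call the trial non-inferiority, yet neither gives a margin or a non-inferiority test. The novice–expert difference in the primary and quality endpoints has no specified interval, although the quantitative endpoints do. These points come from the text and depend on no assumption.

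The size of the consequence does depend on assumptions. At 90% against 97%, the unreported interval runs from clearly below zero (−11.0 to −3.0) to just including zero (−14.5 to +0.5), depending on clustering by novice. The 80% performance-goal test and its joint power statement are not affected. This is a correction that should be made; it does not challenge the primary analysis.

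**What to change.** 1. In the protocol's Study Design statement and in SAP 2.1, replace the non-inferiority label with: performance-goal (80%) study with a paired expert comparison. If the sponsor can point to a margin already prespecified in the full protocol, keep the label and state that margin and its test in the SAP.
2. In SAP 5.4.1 and 5.4.2.1, report the novice-minus-expert difference with a two-sided 95% CI from a paired method that accounts for readers and for clustering by novice.
3. State that, without a prespecified margin, this contrast is descriptive and supports no non-inferiority claim.

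**Cost:** two wording changes and one extra interval per endpoint from data already collected. The non-inferiority label is lost unless a prespecified margin exists. SAP 1 says that protocol 4.2 is IRB-approved and that version 2.0 is approved by the CPP in France, so changing the design statement may need administrative steps for one or both. Sample size and the primary success rule stay as they are.
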